7.3 MEDICAL HISTORY

Medical history will be coded using MedDRA dictionary. A medical history listing will be presented.

8.0 PRIOR AND CONCOMITANT MEDICATIONS

All medications recorded on the CRFs will be coded using the WHO DRUG Dictionary Enhanced. Prior and concomitant medications will be summarized by treatment arm in the safety population by anatomical therapeutic chemical (ATC) Class Level 4 and WHO Drug base substance preferred name.

Prior medications are defined as medications with stop dates occurring before the date of first administration of any study treatment component. Concomitant medications are defined as medications with start dates occurring on or after the date of first administration of any study treatment component and no more than 30 days after the last administration of any study treatment component. Medications with start and stop dates that bracket the date of first administration of any study treatment component will be summarized as both prior and concomitant medications.

Medications that clearly stopped prior to date of first administration of any study treatment component will be included in the prior medications table, and medications that clearly started on or after date of first administration of any study treatment component will be included in the concomitant medications table. All other medications will be included in both the prior and concomitant medications tables.

Prior and Concomitant medication will be summarized for the safety population.

9.0 EFFICACY ANALYSES

Many of the efficacy variables are visual analog scale (VAS) based. Each VAS will be scored as an integer from 0 to 100. When appropriate, VASs will be administered as bipolar measures, meaning

that the neutral point equals 50 (i.e., Drug Liking and Alertness/Drowsiness VAS). The neutral point will also be labeled with an anchor, such as “neither like nor dislike.” Unipolar VASs (i.e., High, Good, Bad, and Any Effects VAS) are presented with anchors such as “not at all” (score = 0) to “extremely” (score = 100), where the neutral point equals 0. The use of unipolar scale is determined by the nature of the subjective effect being measured. If precipitated withdrawal occurs after administration of CAM2038, patients will have a unipolar VAS assessment of opioid withdrawal severity.

The table lists the subjective effects VAS question text and response anchors.

Interpretation	Include Pre-dose	Description	Question Text	Response Anchors
Balance	No	Drug Liking	At this moment, my liking for this drug is	0: Strong disliking 50: Neither like nor dislike 100: Strong liking
Other effects	No	Any Drug Effects	At this moment, I feel any drug effects	0: Not at all 100: Extremely
Positive	Yes	High	At this moment, I feel high	
Positive	No	Good Drug Effects	At this moment, I feel good drug effects	
Negative	No	Bad Drug Effects	At this moment, I feel bad drug effects	
Other Effects	Yes	Desire to use opioids	At this moment, I desire opioids	0: Definitely not 100: Definitely so
Other Effects	Yes	Alertness/Drowsiness	At this moment, my mental state is	0: Very drowsy 50: Neither drowsy nor alert 100: Very alert

9.1 PRIMARY EFFICACY OUTCOME – E_{MAX} DRUG LIKING VAS

The primary efficacy variable will be E_{max} of Drug Liking VAS.

9.1.1 DERIVATION OF E_{MAX} DRUG LIKING VAS

Four hydromorphone challenge sessions (3 consecutive days each with dose randomized) will be conducted on Days 1 to 3, Day 4 to 6, Days 8 to 10, and Days 11 to 13 after the first CAM2038 administration. Each Hydromorphone Challenge Session will consist of 3 doses of hydromorphone 10 mg/mL IM injections (doses of 0 mg [placebo], 6 mg and 18 mg) administered on 3 consecutive days in randomized order. The drug liking VAS will be rated by the subjects at predose and at 5, 10, 15, 30, 45,

60, 75, 90, 120, 150, 180, 210, 240, 270 and 300 minutes post-dose. The primary efficacy variable E_{\max} of drug liking VAS will be the maximum of the above post-dosing drug liking VAS scores.

9.1.2 PRIMARY ANALYSIS

The primary analysis of the primary efficacy variable, E_{\max} of drug liking VAS, will be performed using the completer population. This variable will be analyzed via a mixed model including sequence (ABC, ACB, BAC, BCA, CAB, CBA), dosing (challenge dosing A=0 mg, B=6 mg, or C=18 mg), period (1, 2, or 3 to indicate first, second, or third day of each challenge session), session (challenge session 1, 2, 3, or 4), and dosing-by-session interaction as fixed effects, and subject as random effects. The maximum likelihood estimation will be used to estimate the parameters. Specifically, the following pseudo SAS codes will be used for the analysis:

```
proc mixed data=Efficacy_Data method=ml;
class SubjectID ChallengeDose Sequence Period Session;
model Emax=Sequence ChallengeDose Period Session ChallengeDose*Session;
random SubjectID / Subject= SubjectID;
LSMEANS ChallengeDose*Session/diff cl alpha=0.05;
Run;
```

The estimated treatment effects, differences in treatment effects (test dose – the reference dose of 0 mg), 95% confidence intervals of the differences will be presented. Blockade effects will be claimed if the upper bound of the treatment difference is ≤ 11 .

The same methodology will be used to analyze CAM2038 q1w 24 mg and 32 mg separately.

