4.2 STUDY TREATMENTS

In this study, subjects will be randomized to one of two treatment groups in a 1:1 ratio to receive either CAM2038 1qw 24 mg or CAM2038 1qw 32 mg. Subjects within both CAM2038 1qw dosing groups will be randomized to one of 6 sequences of ordered hydromorphone challenge sessions: A/B/C, A/C/B, B/A/C, B/C/A, C/A/B, and C/B/A, where A, B, and C denote hydromorphone 0 mg, 6 mg, and 18 mg.

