9.1.3 MISSING VALUE IMPUTATION

Missing scores will not be imputed, unless otherwise stated.

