9.1.4 SUPPORTIVE ANALYSES

As a supportive analysis, the primary efficacy variable will be analyzed based on ITT subjects using the same methodology.

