9.6 POWER AND SAMPLE SIZE JUSTIFICATION

A sample size of 24 subjects will provide 90% power for the CAM2038 32 mg to demonstrate no significant difference in the mean E_{\max} score of the Drug Liking VAS comparing to 0 mg hydromorphone at a two-sided 0.05 significance level with a non-significant difference cutoff at ≤ 11 points. In the sample size calculation it was assumed that the true difference was less than or equal to 1.5 and the standard deviation was 9.8.

Additional 24 subjects will be enrolled to CAM2038 24 mg group. This sample size will provide approximately 83% power for the CAM2038 24 mg to demonstrate no significant difference in the mean E_{\max} score of the Drug Liking VAS comparing to 0 mg hydromorphone at a two-sided 0.05 significance level with a non-significant difference cutoff at ≤ 11 points. In the sample size calculation it was assumed that the true difference was less than or equal to 2.5 and the standard deviation was 9.8.

The plan will be to enroll a sufficient number of subjects to ensure that approximately 48 subjects complete the study (24 subjects per treatment group) by over-enrollment as needed.

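### Fitting the primary mixed model by maximum likelihood makes its confidence intervals about 2.5% too narrow: a small effect, but this component always favours the blockade claim

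*SAP*

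**What the plan says.** SAP 9.1.2 fixes the estimation method twice: in the text, "The maximum likelihood estimation will be used to estimate the parameters", and in the code, "proc mixed data=Efficacy_Data method=ml". The model statement, "model Emax=Sequence ChallengeDose Period Session ChallengeDose*Session", has no denominator-degrees-of-freedom option, and subject is the only random effect. Neither document mentions REML, Kenward-Roger or another small-sample adjustment. Protocol 12.3.3.1 describes the mixed model without naming an estimation method.

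Each dose group has its own fit: "The same methodology will be used to analyze CAM2038 q1w 24 mg and 32 mg separately". SAP 9.6 plans for "approximately 48 subjects complete the study (24 subjects per treatment group) by over-enrollment as needed". Blockade is claimed when the upper limit of the two-sided 95% interval for hydromorphone minus 0 mg is at or below 11.

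On missing data, SAP 9.1.3 says "Missing scores will not be imputed, unless otherwise stated". In the only supportive analysis (SAP 9.1.4), "the primary efficacy variable will be analyzed based on ITT subjects using the same methodology".

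**The concern.** ML estimates the residual variance as if the fixed effects were known. REML subtracts the degrees of freedom spent on them. With about 24 subjects per model and 19 fixed-effect parameters, the difference is visible, though not large.

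The direction matters because one rule decides the result: is the upper bound at or below 11? With complete balanced data, ML and REML give the same point estimates and ML only shrinks the standard error. The bound therefore always moves towards the claim, equally for the 6 mg and 18 mg contrasts. SAP 9.4 promises control of the overall Type I error rate at 0.05, and its ordered tests assume that each step is at its nominal level. The supportive ITT analysis reuses the same method, so it would not expose the problem.

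**Working it through.** **Inputs**
- 24 completers per model, SD 9.8, true differences 1.5 (32 mg) and 2.5 (24 mg), margin 11, two-sided 0.05 (SAP 9.6).
- 4 sessions × 3 doses = 12 Emax values per subject (SAP 9.1.1), so 24 × 12 = 288 rows.
- Fixed effects (SAP 9.1.2): intercept 1, sequence 5, dose 2, period 2, session 3, dose-by-session 6, total 19.
- One sequence per subject, as SAP 4.2 suggests: "Subjects within both CAM2038 1qw dosing groups will be randomized to one of 6 sequences of ordered hydromorphone challenge sessions".

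**1. The plan's power figures.** Treat the comparison as two independent samples of 24 with SE = 9.8 × sqrt(2/24) = 2.829, 46 df and one-sided 0.025. The non-central t then gives 90.8% at a difference of 1.5 and 83.7% at 2.5, which matches the stated 90% and 83%. These figures do not depend on the choice between ML and REML.

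**2. Variance divisors.** In the balanced random-intercept model:
- the ML within-subject divisor is 288 − 24 = 264;
- the within-subject fixed effects use 2 + 2 + 3 + 6 = 13 df;
- the unbiased (REML) divisor is 264 − 13 = 251, which agrees with 288 minus the rank of the design matrix including subjects (37).

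The SE ratio, ML to REML, is sqrt(251/264) = 0.975, so the interval is 2.5% too narrow. ML and REML fits to simulated trials gave a mean ratio of 0.975 with complete data and 0.973 with 5% of values missing.

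**3. Sensitivity of the ratio**

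| Case | Divisors | Too narrow by |
|---|---|---|
| One sequence per subject, n = 24 | 251/264 | 2.5% |
| One sequence per subject, n = 30 | 317/330 | 2.0% |
| Sequence redrawn each session, n = 24 | 246/264 | 3.5% |
| Sequence redrawn each session, n = 30 | 312/330 | 2.8% |

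**4. Error at the margin.** With t on 251 df, the critical value is 1.969. ML in effect uses 1.969 × 0.975, and P(t < −1.920) = 2.8% instead of 2.5%. With redrawn sequences it is about 2.9%.

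**5. Shift in VAS points, session-specific contrast**
- 9.8 as residual SD (assumption): REML half-width 1.969 × 2.829 = 5.57; ML 5.43; shift 0.14. With redrawn sequences, about 0.19.
- 9.8 as total SD, assumed intraclass correlation 0.5: residual SD 9.8 × sqrt(0.5) = 6.93, shift 0.10.
- The same at 0.7: residual SD 9.8 × sqrt(0.3) = 5.37, shift 0.08.

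**6. Power cost, residual SD 9.8.** At a difference of 1.5, power is 91.7% under REML and 92.4% under ML. At 2.5 it is 84.9% and 86.0%.

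**7. Other variance the model omits.** The model has no subject-by-dose or subject-by-session term, and the documents give the size of neither. Trials were simulated with the true difference at the margin and total within-subject SD held at 9.8; all shares are assumptions. The SAP model's session-specific error was:

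| Assumed share of within-subject variance | 10% | 25% | 50% |
|---|---|---|---|
| Subject-by-dose only | 3.0% | 3.3% | 4.0% |
| Subject-by-session only | 2.3% | 1.5% | 0.5% |
| Both, each at this share | 2.5% | 1.9% | not run |

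For a contrast pooled over sessions, which the SAP code does not request, subject-by-dose shares of 10% to 50% alone gave 4.9% to 13.3%. A paired t test on within-subject differences stayed at 2.5% in every pattern.

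**The case against.** The strongest reply is that this is too small to matter. Error rises by 0.3 percentage points, and the bound moves by a fraction of a point on a 0–100 integer scale. That is true, and it is why the point is rated as something that should be fixed, not as a threat to the trial.

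The power calculation treats 9.8 as the SD in two independent samples, which suggests a total SD. The smaller shifts of 0.08 to 0.10 points may then be the relevant ones. The power cost also nearly vanishes: at an assumed intraclass correlation of 0.5, 99.7% against 99.8% at a difference of 1.5, and 98.8% against 99.0% at 2.5. This stands. The 2.5% ratio and the 2.8% error rate do not depend on which reading of the SD is right.

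The software default would probably use t on 251 df already, and the SAP calls its code pseudo-code. Both points are fair. But using t instead of z is worth only about 0.5% here and does not repair the variance divisor. The text itself specifies ML.

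The word always needs a limit. It holds for the variance component. With 5% of values missing, ML and REML point estimates differed by up to 0.09 points. Step 7 also shows that omitted variance terms could push the whole model's error either way, so no claim is made about its net error. Nor is the ITT narrowing identical: it shrinks as subjects are added.

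**Conclusion.** The concern holds. As specified, the half-width for each blockade contrast is 2.5% too narrow with 24 balanced completers per group and one sequence per subject. It is 2.0% to 3.5% too narrow across the other cases in the table. The one-sided error of 2.8% assumes that the random-intercept model is otherwise correct. The shift in VAS points depends on how 9.8 is read and on an intraclass correlation the documents do not give. The practical effect is confined to a correct bound just above 11. Even so, the narrowing is one-directional, the documents give no reason for preferring ML, and nothing planned would reveal it. It should be fixed.

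**What to change.** 1. In SAP 9.1.2, replace `method=ml` with `method=reml`, add `ddfm=kr` to the MODEL statement, and reword the estimation sentence to match. With complete balanced data REML does all the work. Kenward-Roger matters for incomplete data, as in the ITT analysis.
2. Add a prespecified sensitivity analysis, leaving the primary model as it is: within-subject differences (hydromorphone minus 0 mg) per session, tested by paired t on n − 1 df. If the deciding contrast is pooled over sessions, use per-subject means. Which contrast decides is a separate question.

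The first change touches two code statements and one sentence, and conflicts with nothing in the protocol. It widens the interval by about 0.14 points or less (about 0.19 if sequences are redrawn each session), which costs about 1 percentage point of power or less. The second adds a short paragraph and one table per dose group. At residual SD 9.8 its half-width is 2.069 × 2.829 = 5.85 points (t on 23 df). It would be wider with period effects, for which it does not adjust.

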Severity of Opioid Withdrawal VAS					X dd		X			
Check-in		X								
Discharge									Xee	

BMI=body mass index; COWS=Clinical Opiate Withdrawal Scale; C-SSRS=Columbia-Suicide Severity Rating Scale; DSM-V = Diagnostic and Statistical Manual of Mental Disorders – Fifth Edition; ECG=electrocardiogram; ET=Early Termination; FSH=Follicle Stimulating Hormone; HIV= Human Immunodeficiency Virus; MADRS=Montgomery-Asberg Depression Rating Scale; OOWS=Objective Opioid Withdrawal Scale; PD=pharmacodynamic VAS=visual analog scale.

- y Blood samples will be taken pre-dose and 1, 4, 6 and 8 hours after CAM2038 q1w injection
- z Blood samples will be taken approximately 60 minutes prior to administration of hydromorphone on each of the 3 Hydromorphone Challenge Session days during the Treatment Phase (i.e., Days 1, 2, 3, 4, 5, 6, 8, 9, 10, 11, 12, and 13).
- aa Blood samples will be taken approximately 168 hours after CAM2038 q1w injection
- bb Pharmacodynamic training may be administered as frequently as required, but all subjects must complete at least one training session prior to the Qualification/Baseline Hydromorphone Challenge Session. Training can only occur prior to or after, but not during the Hydromorphone Challenge Sessions.
- cc On Hydromorphone Challenge Session days (i.e., Day -3, -2, -1, 1, 2, 3, 4, 5, 6, 8, 9, 10, 11, 12, and 13), subjective measures (Drug Liking, Feeling High, Any Drug Effects, Good Drug Effects, Bad Drug Effects, Sedated, Desire to Use Opioids VAS) assessments will be performed at predose (up to 15 minutes prior to dosing) and at 5, 10, 15, 30, 45, 60, 75, 90, 120, 150, 180, 210, 240, 270 and 300 minutes post-dose.
- dd Severity of Opioid Withdrawal VAS will be administered, as needed, if a subject experiences precipitated withdrawal following administration of CAM203 q1w.
- ee Subjects will be discharged on Day 14, if medically acceptable.

Version: 2.0, 17NOV2015 Page 40 of 99

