#### 12.3.3.1. Primary Efficacy Analyses

The primary efficacy variable will be  $E_{max}$  of Drug Liking VAS. This variable will be analyzed via a mixed model including subject, challenge dosing (A=0 mg, B=6 mg, or C=18 mg), Period (1, 2, or 3 to indicate first, second, or third day of each challenge session), challenge session (1, 2, 3, or 4), where subject will be treated as random effects and the remaining parameters fixed effects. The estimated treatment effects, differences in treatment effects (test dose – the reference

Version: 2.0, 17NOV2015 Page 71 of 99

dose of 0 mg), 95% confidence intervals of the differences will be presented. Blockade effects will be claimed if upper bound of the treatment difference is  $\leq 11$ .

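### The primary model leaves out the same-day pre-dose Drug Liking rating and so may give up some precision on the within-subject blockade contrast

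*SAP*

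**What the plan says.** SAP 9.1.2 fits Emax of Drug Liking with "model Emax=Sequence ChallengeDose Period Session ChallengeDose*Session" and a random subject effect, separately in the 24 mg and 32 mg groups. Blockade is claimed when the upper 95% confidence bound for test dose minus 0 mg is at most 11. Protocol 12.3.3.1 describes a similar model without the sequence and interaction terms, "where subject will be treated as random effects and the remaining parameters fixed effects". Neither version has a pre-dose term. Emax is the maximum of the post-dose scores only (SAP 9.1.1).

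The pre-dose rating is scheduled. SAP 9.1.1 states "The drug liking VAS will be rated by the subjects at predose and at 5, 10, 15, 30, 45" minutes and onwards. Footnote cc of Protocol Table 4 covers all the subjective scales on every challenge day: "assessments will be performed at predose (up to 15 minutes prior to dosing".

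The scale table in SAP 9.0 disagrees. Its column on pre-dose inclusion reads No for Drug Liking and for Any, Good and Bad Effects, and Yes only for High, Desire to use and Alertness/Drowsiness. The protocol's Summary of Changes says this column was removed from Protocol Table 6 because all pharmacodynamic measures are taken pre-dose, and the current Table 6 does not have it. The SAP column therefore looks like a leftover.

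**The concern.** The decision rests on one confidence bound per comparison, and SAP 9.4 tests four comparisons in fixed order, so a miss at one step blocks every later claim. Interval width matters at each step.

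The random subject effect removes only what is constant across a subject's challenge days. Gender and the Qualification Phase response are also constant within a subject and cancel from a within-subject dose contrast. The same-day pre-dose rating is different. It is collected already, it precedes that day's injection, and it can track day-to-day variation in how a subject rates liking at that moment. If it does, leaving it out makes the interval wider than it has to be.

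**Working it through.** **Inputs (SAP 9.6 and 9.1.2).** 24 completers per CAM2038 group; SD 9.8; true difference 1.5 (32 mg) or 2.5 (24 mg); margin 11; two-sided 0.05, so 0.025 on the upper side. Stated power is 90% and about 83%. The within-subject correlation rho between pre-dose rating and Emax is not given; 0 to 0.5 is an assumed range.

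**Reproducing the stated power.** Treat the test-dose and 0 mg scores as independent sets of 24:

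- SE = 9.8 × sqrt(2/24) = 2.83, with 46 degrees of freedom.
- Noncentrality: (11 − 1.5)/2.83 = 3.36 and (11 − 2.5)/2.83 = 3.00.
- Power from the noncentral t: 90.8% and 83.7%, which match.

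The stated power therefore takes no credit for pairing within subject or for a covariate.

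**Adding the covariate.** The SE is multiplied by sqrt(1 − rho²), and one residual degree of freedom is lost (46 to 45).

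| rho | SE factor | 95% half-width | Power 32 mg | Power 24 mg |
|---|---|---|---|---|
| 0 | 1.000 | 5.70 | 90.8% | 83.6% |
| 0.1 | 0.995 | 5.67 | 91.0% | 84.0% |
| 0.2 | 0.980 | 5.58 | 91.8% | 85.1% |
| 0.3 | 0.954 | 5.44 | 93.1% | 86.9% |
| 0.4 | 0.917 | 5.22 | 94.8% | 89.4% |
| 0.5 | 0.866 | 4.93 | 96.7% | 92.4% |

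A simulation of the 24-subject, four-session, three-dose layout (3,000 runs per setting, intra-subject correlation 0, 0.3 or 0.5) agrees. SE ratios were about 1.00 at rho 0, 0.996 to 1.000 at 0.1, 0.95 to 0.96 at 0.3, and 0.85 to 0.89 at 0.5.

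**Other readings of 9.8.** The documents do not say which SD this is.

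- SD of the paired difference: SE = 9.8/sqrt(24) = 2.00. Power is already 99.5% and 98.2%, rising to 99.95% and 99.7% at rho 0.5.
- Residual SD with the dose contrast pooled over four sessions: SE = 9.8 × sqrt(2/96) = 1.41. Power is above 99.9% in both groups with no covariate.

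**Carryover.** Within a session, 0 mg directly follows 18 mg in two of the six sequences (BCA, CAB), and 18 mg never follows itself. Suppose, for illustration only, that 18 mg raises the next morning's pre-dose rating by 3 points. The mean pre-dose rating is then 3 × 2/6 = 1 point higher on 0 mg days than on 18 mg days. With covariate slope b, adjustment adds b × 1 to the 18 − 0 contrast. Take a true contrast of zero:

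- Carryover of the same size in Emax as well: unadjusted −1, adjusted −1 + b. The unadjusted result leans towards a blockade claim, and adjustment moves it back.
- Carryover in the pre-dose rating only: unadjusted 0, adjusted +b. For an assumed b of 0.5 to 1.0, that is 0.5 to 1.0 points against a claim.

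**The case against.** The strongest reply is that the planned model is valid and the benefit is conjecture. Protocol and SAP agree on having no pre-dose term, and leaving out a covariate does not bias the randomised contrast. No correlation is given. Before the injection, the item asks about liking for a drug not yet received that day, on a scale with neutral point 50. Protocol 8.3 also admits only subjects whose placebo rating lies between 40 and 60. Both facts suggest pre-dose scores may cluster near neutral and predict little. At a correlation of 0.3 or less the gain is at most about 2 to 3 percentage points of power. All of this stands, and it makes the point an optional improvement.

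The second reply is that the covariate has a cost, because on days 2 and 3 of a session it follows the previous day's randomised dose. This stands in part. The possible shift is small beside the 11-point margin. When carryover reaches Emax too, it is the unadjusted contrast that is distorted. Reporting both fits would show any shift.

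A reader might infer more: that the primary analysis is biased, that the trial is underpowered without the covariate, or that the SAP table shows the rating is not collected. The documents support none of these. Randomised dose order protects the contrast from bias due to the omission, the stated power reproduces without a covariate, and SAP 9.1.1 and Table 4 both schedule the pre-dose rating.

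**Conclusion.** A scheduled same-day baseline goes unused in the primary model, which may cost precision. The reduction in SE ranges from nothing at a correlation of 0, through 0.5% at 0.1 and about 5% at 0.3, to about 13% at 0.5. In power terms, under the plan's own formula, the 24 mg group gains from about zero to nearly 9 percentage points over that range (83.7% to 92.4%) and the 32 mg group up to about 6 (90.8% to 96.7%).

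Those upper figures need a correlation that the documents do not provide, and they need 9.8 to act as a residual SD for a single-session contrast with no pairing credit. If it is the SD of the paired difference, the gain is at most about 0.4 and 1.5 points. The point is minor and low in certainty, but cheap to act on. The disagreement between SAP 9.0 and SAP 9.1.1 on pre-dose Drug Liking needs correcting whatever is decided about the model.

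**What to change.** Before database lock and unblinding:

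1. In SAP 9.1.2, add the same-day pre-dose rating as a fixed covariate in two parts: the subject's mean pre-dose rating, and that day's deviation from it. The split keeps between-subject and within-subject slopes apart; only the deviation can sharpen the dose contrast.
2. Treat the secondary VAS analyses in the same way.
3. Report the unadjusted fit alongside, and state in advance which fit decides the claim.
4. State how a challenge day with no pre-dose rating is handled. SAP 9.1.3 imputes nothing, so as written such a day would drop out of the adjusted model.
5. Align the pre-dose column of the SAP 9.0 scale table with SAP 9.1.1 and Protocol Table 4.

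The cost is a few lines of SAP text and code, one or two degrees of freedom, possible loss of days with a missing pre-dose rating, and a possible small shift in the contrast if the previous day's dose carries over into the pre-dose rating alone. No additional data are required.

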# 8.3. Qualification Criteria

In addition to the inclusion and exclusion criteria, subjects must meet each one of the following criteria in order to be eligible for participation in the Treatment Phase:

- Maximum effect (Emax) in response to IM hydromorphone 6 mg greater than that of placebo on Drug Liking bipolar VAS (response to hydromorphone 6 mg should be greater than 55 mm in the VAS and a difference of at least 15 mm between placebo and 6 mg) and acceptable overall responses to hydromorphone and placebo on the subjective measures, as judged by the Investigator or designee.
- Emax in response to IM hydromorphone 18 mg greater than that of placebo on Drug Liking bipolar VAS (greater than 60 mm and a difference of at least 20 mm between placebo and 18 mg) and Emax score of at least 20 points, and acceptable overall responses to hydromorphone and placebo on the subjective measures, as judged by the Investigator or designee.
- Acceptable placebo response based on Drug Liking bipolar VAS (score between 40 and 60 mm, inclusive).
- Subject is able to tolerate IM hydromorphone 6 mg and 18 mg, as judged by the Investigator, including ability to complete most pharmacodynamic assessments administered within 5 hours post-dose.
- General behavior suggests that the subject could successfully complete the study, as judged by the research site staff.

Version: 2.0, 17NOV2015 Page 46 of 99

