6.0 GENERAL CONVENTIONS

Unless otherwise stated, all analyses will be performed using SAS Version 9 and all hypothesis tests will be conducted at a two-sided significance level of 0.05. P-values will be presented with 3 decimals and p-values that are less than 0.001 will be presented as <0.001.

Continuous (non survival related) data will be summarized using descriptive statistics: number of observations (n), mean, standard deviation (SD), median, minimum, and maximum. Frequencies and percentages will be used to summarize categorical (discrete) data. Presentations of categorical data will generally suppress percentages for items where the count is zero in order to draw attention to the nonzero counts. In general, mean, standard deviation, median, minimum, maximum, and percentages will be presented with one decimal.

Unless otherwise stated, confidence intervals, when presented, will be constructed at the two-sided 95% level.

Summaries of plasma concentrations of BPN and norbuprenorphine will be presented for the Completer population by treatment group. The following descriptive statistics will be presented at each nominal time point: n, arithmetic mean, SD, coefficient of variation percentage (CV%), median, geometric mean, geometric CV%, minimum and maximum values. Individual plasma concentrations of BPN and norbuprenorphine will be listed for the Safety population by treatment group. Mean plasma concentration-time data will be displayed for the Completer population in linear and semi-logarithmic scales.

The pharmacokinetic parameter data will be listed and summarized by treatment for the Completer population. Summary statistics will include n, arithmetic mean, SD, CV%, median, geometric mean, geometric CV%, minimum and maximum values.

Data listings will present all data collected on CRFs by study drug, center, and subject number.

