9.4 ADJUSTMENTS FOR MULTIPLICITY

The study involves multiple comparisons. Procedures will be used to control for the overall Type I error rate at the significance level of 0.05. The following ordered comparisons of blocking effect will be tested at the 0.05 level of significance:

1. Hydromorphone 6 mg vs Hydromorphone 0 mg for CAM2038 q1w 32 mg;
2. Hydromorphone 6 mg vs Hydromorphone 0 mg for CAM2038 q1w 24 mg;
3. Hydromorphone 18 mg vs Hydromorphone 0 mg for CAM2038 q1w 32 mg;
4. Hydromorphone 18 mg vs Hydromorphone 0 mg for CAM2038 q1w 24 mg;

Blockade effect cannot be claimed unless all preceding blocking effects, if any, are established.

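### The primary model allows only a random subject intercept and one residual variance, so the upper bound that decides the 18 mg blockade claim may be too low.

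*SAP*

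**What the plan says.** SAP 9.1.2 fits one mixed model per CAM2038 group to the Drug Liking Emax values of completers. The estimation line is "proc mixed data=Efficacy_Data method=ml", the fixed effects are "model Emax=Sequence ChallengeDose Period Session ChallengeDose*Session", and the only random term is "random SubjectID / Subject= SubjectID". In PROC MIXED that term is a random intercept for subject. There is no REPEATED statement, GROUP= option, subject-by-dose term, robust standard error or Kenward-Roger option. All 12 Emax values of a subject therefore share one residual variance and one common correlation.

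Protocol 12.3.3.1 has the same covariance, "where subject will be treated as random effects and the remaining parameters fixed effects", but no dose-by-session interaction. The supportive ITT analysis (SAP 9.1.4) repeats the SAP method, so no planned analysis uses another covariance.

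Blockade is claimed when the upper limit of the 95% interval for test dose minus 0 mg is at most 11. The code requests "LSMEANS ChallengeDose*Session/diff cl alpha=0.05", which gives dose differences within each session. The testing order in SAP 9.4 instead lists a single comparison per dose and group, for example "Hydromorphone 18 mg vs Hydromorphone 0 mg for CAM2038 q1w 32 mg", and names no session.

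**The concern.** The model leaves out two features.

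- **Subject-by-dose variation.** Some subjects may be less well blocked than others at a given dose, session after session. Protocol Tables 2 and 3 give geometric CVs for buprenorphine of 45% (Cmax) and 24% (day-7 concentration) after a single 32 mg dose, and 44% and 24% (steady-state maximum and average) at 16 mg. A secondary objective is to explore how concentration relates to blockade. If that relation exists, such variation is likely. With four replicates per dose it can be estimated, but the model sets it to zero.
- **Unequal spread by dose.** Protocol 8.3 requires "Acceptable placebo response based on Drug Liking bipolar VAS (score between 40 and 60 mm, inclusive", while the 18 mg response has only lower limits. This is a hint that 18 mg may vary more than placebo, but no more than a hint.

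The claim rests on an upper confidence limit, so any error in the standard error passes straight into the false-claim rate. SAP 6.0 states that "all hypothesis tests will be conducted at a two-sided significance level of 0.05", so the nominal one-sided rate for this bound is 2.5%.

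**Working it through.** **Inputs from the documents.** 24 completers per group, four sessions of three doses, margin 11, SD 9.8, true differences 1.5 (32 mg) and 2.5 (24 mg), stated power 90% and about 83% (SAP 9.6).

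**Inputs assumed.** All dose-specific SDs and all subject-by-dose variances. The documents give neither.

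**1. The plan's own figure.** SE = 9.8 × √(2/24) = 2.829. The noncentralities are (11 − 1.5)/2.829 = 3.358 and (11 − 2.5)/2.829 = 3.005. A two-sample t calculation with 46 df gives 90.8% and 83.7%, so the stated power is reproduced. It uses one SD for all doses and treats the doses as independent samples.

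**2. Effect of ML alone.** There are 24 × 11 = 264 within-subject df. The model spends 2 (dose) + 3 (session) + 6 (interaction) + 2 (period) = 13, leaving 251. ML divides by 264, so the residual variance is low by a factor of 251/264 = 0.951. The false-claim rate becomes about 2.8% by formula and 2.7% in simulation, even when every variance assumption holds.

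**3. Unequal residual variances.** With variances a, b, c at 0, 6 and 18 mg, the model uses (a+b+c)/3 where the 18 mg contrast needs (a+c)/2. The standard error is too small only if a + c > 2b. Ignoring the ML effect, the rate is 1 − Φ(1.96 × √ratio), with ratio = [2(a+b+c)/3]/(a+c). For SDs 5/8/14: 2 × 285/3 = 190, and 190/221 = 0.860, giving 3.5%. For 8/12/10: 205.3/164 = 1.252, giving 1.4%.

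**4. Subject-by-dose variance.** Let T be common to the doses and S the residual variance. Each subject contributes 4 × 2T = 8T to the within-subject sum of squares on 11 df, so the model uses S + (8/11)T.
- Per session, the contrast needs S + T.
- Averaged over sessions, the model uses (S + (8/11)T)/4 where S/4 + T is needed.

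With T half of S + T = 1, the per-session ratio is 0.864 (3.4%). The averaged ratio is 0.216/0.625 = 0.345 (12.5%).

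If T differs by dose, 8T is replaced by 4 × (2/3) × the sum of the three variances. For residual SD 9.8 and subject-by-dose SDs 0/4/6, the model variance is 96.04 + 4 × (2/3) × 52/11 = 108.65. The averaged 18 mg ratio is (108.65/2)/(48.02 + 36) = 0.647, or 5.8% before the ML effect and about 6% with it.

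**5. Simulated false-claim rates, 18 mg versus 0 mg.** True difference 11, ML random-intercept model, 20,000 trials per scenario. SDs are in the order 0/6/18 mg.

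| Assumption | Per session | Averaged over sessions |
|---|---|---|
| Equal variances, no subject-by-dose effect | 2.7% | – |
| Residual SD 4.9/9.8/14.7 | 3.3% | – |
| Residual SD 5/8/14 | 3.9% | – |
| Residual SD 5/5/15 | 4.9% | – |
| Residual SD 8/12/10 | 1.6% | – |
| Subject-by-dose share 25/50/75% | 3.3/3.9/4.8% | 8.1/13.3/17.8% |
| Both: residual 7/7/7, subject-by-dose 0/3/8 | 4.0% | 11.6% |
| Both: residual 3/4/9, subject-by-dose 1/2/11 | 6.8% | 18.3% |

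An extreme residual pattern of 1/1/17 gives 6.0% per session.

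**6. The 6 mg test.** Under residual SDs 5/5/15 its per-session rate is 0.02%, which is very conservative. With subject-by-dose shares of 25/50/75% its averaged rate is 8.0/12.9/18.0%, which is inflated.

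**7. Allowing for both features.** Each contrast was re-analysed as a period-adjusted within-subject difference with its own between-subject variance (21 df). The 18 mg rate was then 2.3-2.6% in every scenario, per session and averaged.

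**The case against.** A reader might infer that the 18 mg error rate is inflated as a matter of fact. The documents do not show that. The only SD they give is 9.8, and the direction depends on variances that nobody has stated: with 6 mg most variable, the rate falls below nominal.

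The qualification limits are weak evidence. They apply before CAM2038, the scale is capped at 100, and Protocol 9.4 expects attenuated responses once buprenorphine is on board. They do not make equal spread implausible under treatment.

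The contrast that the SAP code actually produces is the per-session one, where the effect is modest and part of the excess comes from ML. If a claim required all four sessions to pass, and every true difference were 11, the rate would be 0-1.1%. That protection goes if one session sits at 11 and the others lie well below. The larger averaged figures rest on the protocol model, and Protocol 12 says its methods may be revised, with the SAP as the final plan.

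All of this limits the size of the claim. It does not remove the point: SAP 9.4 still lists one comparison per dose, so the averaged contrast remains a fair reading, and nothing in either document relaxes the covariance. It is also tempting to say that the 6 mg gate loses power, but that holds only for some variance patterns; averaged over sessions with subject-by-dose variation, the 6 mg test can be too liberal.

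**Conclusion.** The concern holds in conditional form. The planned covariance is valid only if the doses share one variance and subjects do not differ consistently in how well each dose is blocked. The plan neither supports those assumptions nor tests them.

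Under the assumed values, the 18 mg false-claim rate is about 3-5% per session when one feature is present and up to about 7% when both are strong. It is about 6-18% for a session-averaged difference with subject-by-dose variation. It is close to nominal (2.7%) if the assumptions hold and about 1.6% if 6 mg is the most variable dose. Subject-by-dose variance common to the doses always makes the standard error too small. Unequal residual variance does so for 18 mg only when the 0 and 18 mg variances together exceed twice the 6 mg variance.

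These figures show what could happen; they do not predict the trial. The change is worth making because it protects the deciding bound whichever variances turn out to hold.

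**What to change.** In SAP 9.1.2:

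- replace ML with REML and Kenward-Roger degrees of freedom;
- add a random subject-by-dose term beside the subject intercept;
- allow residual variance by dose (`REPEATED / GROUP=ChallengeDose`);
- state a fallback for non-convergence that still covers both features, such as a period-adjusted within-subject difference for each dose contrast with its own between-subject variance;
- apply the model to the contrast that decides the claim, and say which one that is.

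The simulated 2.3-2.6% was obtained with the fallback analysis, not with the extended mixed model. A single common subject-by-dose variance may not fit fully if that variance itself differs strongly by dose; the fallback does not have that limit.

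The cost is a SAP text and code change and a few more variance parameters from 24 subjects per group. If 18 mg is more variable, power also falls. At a true difference of 1.5, per-session 18 mg power under the fallback is 80% (residual SDs 5/5/15), 85% (5/8/14) and 81% (4.9/9.8/14.7). The planned model gives 90%, 91% and 87% in the same scenarios, and the stated figure for a common SD of 9.8 is 90%.
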